### 10.2. Treatment Compliance

Study medication is to be administered twice daily, and compliance is recorded in the eDiary as full (both doses), partial (less than full daily dose) or missed (both doses) each day. From this, compliance will be calculated by assuming that a missed dose=0% of dose consumed, partial=50% of dose consumed, and full=100% of dose consumed. For each subject, a daily compliance score will be thus obtained.

Compliance will be summarized for the SAF and mITT populations over the course of T+M and Maintenance only, reported by treatment group.

### 10.3. Adverse Events

An AE is defined as any unfavorable and unintended sign (including an abnormal, clinically significant laboratory finding), symptom, or disease temporally associated with the use of a medicinal (investigational) product, whether or not considered related to the medicinal (investigational) product. The period of observation for adverse events extends from the time the subject gives informed consent until the end of the titration/transition period (Visit 13). For patients who continue into the open-label extension study, AEs of special interest will continue to be monitored for up to 6 months after the last dose of study medication.

A TEAE is defined as any AE that based on start date information occurs after the first intake of study treatment. Safety tables will present TEAE data by assigned treatment group through Visit 13. All other AEs occurring after enrollment and prior to the first administration of study treatment are defined as non-treatment emergent AEs (non-TEAEs).

AEs are categorized as related or unrelated. If the AE is thought to be definitely, probably or possibly related to study drug then it is to be categorized as related. Possibly or definitely unrelated is categorized as unrelated. Any missing relationship will be considered as "related."

The severity of AEs (whether nonserious or serious AEs) will be assessed by the investigator as follows:

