### 2.3. Brief Description

Both Study 1501 and Study 1502 are multicenter, double-blind, parallel-group, placebo-controlled studies designed to assess the efficacy, safety, and PK of ZX008 when used as adjunctive therapy in pediatric and young adult subjects with Dravet syndrome. Study 1501 was conducted at approximately 30 study sites in North America; Study 1502 was conducted at approximately 30 study sites in Europe, Australia, and Japan. For Study 1502 Japan was added in 2019 whereas Europe and Australia started in 2015. Approximately 36 sites will contribute randomized subjects to Study 1502.

The expected study period of 22 weeks comprises a Baseline period (6 weeks), a Treatment period (14 weeks) (2 weeks titration + 12 weeks maintenance), and a Post Dosing visit 2 weeks after study completion or early termination.

Upon study completion, eligible subjects will be able to receive ZX008 in an open-label extension study for up to 1 additional year of treatment. There will be cardiac safety follow-up of 3 to 6 months after study drug discontinuation for early termination or for subjects who complete the study but do not enroll in the open-label extension study. Subjects from France, Germany and the Netherlands will have a cardiac safety follow-up visit approximately 24 months after the last dose of active study medication. Follow-up safety visit results will be reported separately.

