### Incidence of Treatment Emergent Adverse Events

The following summaries will display the number and percentage of subjects with an adverse event as well as the corresponding number of events by system organ class (SOC) and preferred term (sorted alphabetically):

- All TEAEs
- Serious TEAEs
- TEAEs by Maximum Severity
- Study Drug Related TEAEs
- All AEs that lead to premature discontinuation from the study

Additional summary tables will tally the number and percent of subjects in each treatment group who experience an AE that occurs in at least 2%, and at least 5%, of subjects. The summary will be presented by preferred term in decreasing order of incidence.

This document is confidential.

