**Statistical Analysis Plan**

Sponsor: Zogenix International Limited; Protocol No.: ZX008 Study 2 (ZX008-1501 and ZX008-1502)

Table	14.3.1.2b	Treatment-Emergent Adverse Events by MedDRA System Organ Class and Preferred Term (Non-Japan) – Safety Population
Table	14.3.1.3	TEAEs Leading to Study Discontinuation by Primary SOC and PT – Safety Population
Table	14.3.1.3a	TEAEs Leading to Study Discontinuation by Primary SOC and PT (Japan) – Safety Population
Table	14.3.1.3b	TEAEs Leading to Study Discontinuation by Primary SOC and PT (Non-Japan) – Safety Population
Table	14.3.1.4	Serious TEAEs by Primary SOC and PT – Safety Population
Table	14.3.1.4a	Serious TEAEs by Primary SOC and PT (Japan) – Safety Population
Table	14.3.1.4b	Serious TEAEs by Primary SOC and PT (Non-Japan) – Safety Population
Table	14.3.1.5	Related TEAEs by Primary SOC and PT – Safety Population
Table	14.3.1.5a	Related TEAEs by Primary SOC and PT (Japan) – Safety Population
Table	14.3.1.5b	Related TEAEs by Primary SOC and PT (Non-Japan) – Safety Population
Table	14.3.1.6	TEAEs by Maximum Severity by SOC and PT– Safety Population
Table	14.3.1.6a	TEAEs by Maximum Severity by SOC and PT (Japan) – Safety Population
Table	14.3.1.6b	TEAEs by Maximum Severity by SOC and PT (Non-Japan) – Safety Population
Table	14.3.1.7	Treatment-Emergent Adverse Events Occurring in $\geq 5\%$ of Subjects by MedDRA System Organ Class and Preferred Term - Safety Population
Table	14.3.1.7a	Treatment-Emergent Adverse Events Occurring in $\geq 5\%$ of Subjects by MedDRA System Organ Class and Preferred Term (Japan) - Safety Population
Table	14.3.1.7b	Treatment-Emergent Adverse Events Occurring in $\geq 5\%$ of Subjects by MedDRA System Organ Class and Preferred Term (Non-Japan) - Safety Population
Table	14.3.1.8	Overview of Number of Subjects with Treatment-Emergent Adverse Events of Special Interest – Safety Population
Table	14.3.1.8a	Overview of Number of Subjects with Treatment-Emergent Adverse Events of Special Interest (Japan) – Safety Population
Table	14.3.1.8b	Overview of Number of Subjects with Treatment-Emergent Adverse Events of Special Interest (Non-Japan) – Safety Population
Table	14.3.1.9	Treatment-Emergent Adverse Events of Special Interest (AESI) by SOC and PT – Safety Population
Table	14.3.1.9a	Treatment-Emergent Adverse Events of Special Interest (AESI) by SOC and PT (Japan) – Safety Population

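### Treatment-emergent status depends on start date alone, so a baseline adverse event that worsens or becomes serious on treatment under its original record is left out of the by-arm safety tables

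*SAP*

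**What the plan says.** The Study 2 SAP, section 10.3, defines treatment emergence by onset: "A TEAE is defined as any AE that based on start date information occurs after the first intake of study treatment". It then places the remainder: "All other AEs occurring after enrollment and prior to the first administration of study treatment are defined as non-treatment emergent AEs (non-TEAEs"). Section 6.4.1 of the Study 1 SAP has the same two sentences. Neither plan has a provision for an event that is present before dosing and worsens afterwards.

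Pre-dose events will be in the database. Section 10.3 states: "The period of observation for adverse events extends from the time the subject gives informed consent". Section 2.3 gives the length of that window: "The expected study period of 22 weeks comprises a Baseline period (6 weeks").

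The comparison between arms is then confined to TEAEs: "Safety tables will present TEAE data by assigned treatment group through Visit 13". The table index (Study 2 SAP section 15) agrees. Two examples are Table 14.3.1.4, "Serious TEAEs by Primary SOC and PT – Safety Population", and Table 14.3.1.6, "TEAEs by Maximum Severity by SOC and PT– Safety Population". The overview, SOC and preferred-term, related, AESI and discontinuation tables are also titled for TEAEs, as they are in Appendix 1 of the Study 1 SAP. The one mismatch is in the text of section 10.3, which lists a summary of "All AEs that lead to premature discontinuation from the study" while the index title for that table (14.3.1.3) covers TEAEs only.

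**The concern.** Aggravation of a condition that the child already has is an ordinary form of drug toxicity. Under a start-date rule, an event recorded as mild in week 4 of baseline and as severe or serious in week 3 of treatment has a pre-dose start date. It therefore fails the flag for the TEAE, serious-TEAE and maximum-severity tables. The by-arm tables carry the safety comparison, and a listing gives no incidence by arm. If ZX008 aggravates existing events more often than placebo does, that difference cannot be seen where a reader will look for it.

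The rule also sits uneasily with the rest of the plan. The AESI definition of dyspnea sets aside a previous condition only when it has not worsened (Table 5 in Study 1, Table 6 in Study 2), so the plan itself treats worsening as relevant. Yet the AESI tables require the TEAE flag. Elsewhere the plan leans towards counting: missing severity is taken as severe, missing relationship as related, and missing dates are imputed so that a possible TEAE is treated as one.

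**Working it through.** The plan states no figure for this point, so there is nothing to reproduce. The check sets the rules side by side and then gives a scale.

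**Tracing one event.** Take an adverse event with a complete start date in baseline, mild before dosing, severe or serious after first dose, and kept under one record.

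1. Collected? Yes, because collection runs from consent.
2. TEAE? No. The start date precedes first intake, and post-dose severity plays no part in the definition.
3. In the overview, SOC and preferred-term, serious, maximum-severity, related or AESI tables? No, because all are TEAE tables.
4. In the discontinuation table, if the child withdraws because of it? Yes by the text of section 10.3, no by the index title.
5. In the death row of the overview, if it is fatal? Study 1 section 6.4.1.1 has a row for death without a TEAE limit. The Study 2 overview limits the row to TEAEs.
6. In the listings? Yes. All AEs, serious AEs, AEs leading to discontinuation and deaths are listed for all enrolled subjects.

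**Exception.** Under the date rules (Study 1 section 6.1.7, Study 2 section 6.4), a partial start date in the month, or year, of first dose is imputed to the first dose date and is meant to be handled as a TEAE. So some baseline events are counted. These rules also turn on start date only.

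**Effect on the comparison.** Let w(Z) and w(P) be the fractions of the ZX008 and placebo arms whose only event of a given kind is a baseline event that worsens after first dose under its original record.

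- Reported difference = difference with worsening counted − [w(Z) − w(P)].
- If w(Z) = w(P), both arms are under-counted and the difference is unchanged.
- If w(Z) > w(P), a ZX008 excess of w(Z) − w(P) is hidden.

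**Scale.** Both studies plan 40 per arm.

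- One child: 1/40 = 2.5%.
- Two children: 2/40 = 5.0%.
- Section 10.3 of the Study 2 SAP uses display thresholds of 2% and 5%, and the table of events more frequent on ZX008 than placebo uses 2%. One uncounted child exceeds the lower threshold and two reach the upper.
- Illustration, with assumed counts: two such children on ZX008 and one on placebo hide 5.0 − 2.5 = 2.5 points of difference.

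The documents give no rate of baseline events or of worsening, so w(Z) and w(P) cannot be estimated from them.

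**The case against.** The strongest objection is that the loss depends on a recording convention that is not shown. If the protocol or CRF instructions require a new record with a new start date when an event worsens, the start-date rule already counts it. That stands as a condition on the point. It does not remove the point, because neither SAP states or relies on such a convention.

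Second, much worsening is compared by arm elsewhere: laboratory changes including specific platelet and prolactin summaries, vital signs and weight, neurological and C-SSRS shift tables, status epilepticus modelled with baseline status, and ECG and ECHO changes. Several AESIs (blood pressure, heart rate, glucose) are themselves defined relative to Screening or Day -1. This narrows the gap. It does not restore a worsened event as a severe or serious adverse event by arm.

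Third, adverse events are not tested inferentially, so no decision rule is affected. That is correct. The issue is descriptive under-counting.

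Two stronger readings are tempting. A reader might infer that the loss is one-sided and falls only on ZX008. The documents do not support that: the rule is the same for every arm, baseline events on placebo can worsen too, and only the excess is hidden. A reader might also size the loss by assuming that 10 to 20% of children start dosing with an ongoing event of a given kind and that 20 to 40% of those worsen, which gives 0.10 × 0.20 = 2% to 0.20 × 0.40 = 8% of an arm. Neither input has a source in the documents and nothing is subtracted for placebo, so the result does not measure a lost contrast.

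**Conclusion.** The point holds as a gap in a stated definition. In both SAPs a baseline-onset event that increases in severity or becomes serious after first dose is a non-TEAE and is absent from the by-arm TEAE tables. This rests on two conditions: the worsening stays under the original record, and the start date is not a partial one imputed to first dose. The events are not lost from the report, because they remain in the listings.

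The consequence is under-counting in all arms. A ZX008 excess is hidden only so far as worsening is more common on ZX008 than on placebo. The size is unknown. At 40 per arm a single child is 2.5%, which is enough to matter for tables with a 2% display threshold. The definition should be corrected, but the documents give no ground for saying that the safety comparison is materially biased.

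**What to change.** In section 10.3 of the Study 2 SAP, define a TEAE as an adverse event that starts on or after first dose, or that starts before first dose and increases in severity or becomes serious on or after first dose. For the second kind, tabulate the post-dose severity and use the date of worsening as onset where it is recorded, or the start date of a new record opened at worsening. State which of these the data collection supports. The on-or-after wording also makes the definition agree with imputing partial dates to the first dose date.

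Reconcile the discontinuation summary in section 10.3, worded for all AEs, with its TEAE-only index title.

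Study 1 has already been reported (Study 2 SAP section 2.3), so amending section 6.4.1 would not be prospective. Add a supplementary Study 1 tabulation under the same definition so that the two studies stay comparable.

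The cost is one clause, one flag derivation and one supplementary table, with slightly higher TEAE counts. Dating the worsening needs dated severity changes or new records, and the SAP does not show whether these are collected. Section 11 places Study 2 unblinding after data cleaning, so the change can be made while the data are still blinded.

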**Transition Period:**

Subjects who completed the Maintenance Period and were continuing into the open-label extension study were to be transitioned from double-blind study medication to open-label ZX008 (Table 3). Study medication was administered as equal doses BID in the morning and in the evening approximately 12 hours apart, with food. Each dose should have been separated by a minimum of 8 hours and a maximum of 12 hours. A missed dose of study medication may have been taken later up to 8 hours before the next scheduled dose; otherwise, the missed dose should not be given. Study medication was administered using the oral dosing syringe provided.

All subjects entering the open-label extension study were transitioned from their blinded daily dose (placebo, 0.2 mg/kg/day, 0.8 mg/kg/day, or 30 mg/day) to the 0.2 mg/kg dose during the 2-week interval between Visits 12 and 13, without breaking the blind. The IWR system assigned two bottles of IMP to the subject, one for each step in the transition. A new bottle of IMP was started by the subject at each level of the transition step.

Table 3. Transition Algorithm

Dose Group in Double-Blind Study	Transition Step 1 Day 1-4 after Visit 12	Transition Step 2 Days 5-14 after Visit 12
ZX008 0.2 mg/kg/day	ZX008 0.2 mg/kg/day	ZX008 0.2 mg/kg/day
ZX008 0.8 mg/kg/day	ZX008 0.4 mg/kg/day	ZX008 0.2 mg/kg/day
Placebo	ZX008 0.2 mg/kg/day	ZX008 0.2 mg/kg/day
Note: maximum daily dose of ZX008 is 30 mg.		

Subjects who had been randomized to placebo increased their dose to 0.2 mg/kg/day beginning on Day 1 of the transition (the day following Visit 12.) Subjects who had been randomized to 0.2 mg/kg/day continued to receive that dose. Subjects who had been randomized to 0.8 mg/kg/day or were receiving the maximum dose of 30 mg/day decreased to a dose of ZX008 0.4 mg/kg/day, or a maximum of 30 mg/day. After 4 days at this dose level (Day 5), these subjects decreased their dose to 0.2 mg/kg/day. Subjects were to report to the clinic on Day 15 for enrollment into the open-label extension study.

Data from the Taper or Transition period will not be included towards the planned efficacy endpoints except where specified, but will be included in the safety analyses.

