**6.5. Visit Windows**

The following rules will be used to window data into treatment periods for by treatment period tabulations. For all by-visit tabulations, the nominal visit as recorded on the CRF will be used.

Double Blind Treatment Period	
The Double-Blind Treatment Period start date is the date of first treatment, Study Day 1 (ie, the day after V3). The Double-Blind Treatment Period end date is the last date the patient was on study treatment.
 
The Double-Blind Treatment Period consists of 16 weeks from first treatment start date, which includes 2 weeks of Titration period, 12 weeks of Maintenance period and 2 weeks of Taper/Transition period; therefore the end date would be considered the date at Visit 13.
 
For subjects who discontinue early from the study, the double-blind treatment period end date will be the date at the early termination visit (Visit 12).

Titration Period	
The Titration Period covers the first 14 ± 4 days of treatment while subjects are titrated to their randomized dose. It begins on the first day of treatment (Study Day 1) and extends through Visit 6 (when the patient has reached their randomization dose). The Titration Period applies to all subjects including placebo recipients. If a subject withdraws from the study prior to treatment in the maintenance period, all safety assessments and events up to and including the date of study withdrawal will be tabulated in the titration period.

Maintenance Period	
The Maintenance Period covers the 12 weeks following the end of the titration period. It begins on the date of Visit 6 + 1 day and extends through the end of study/early termination visit (Visit 12).

Titration + Maintenance Period (T+M)	
The T+M period combines the Titration and Maintenance periods, beginning on the date of first treatment (Study Day 1) and extending to the end of study/end of treatment visit. The T+M period is considered the treatment period.

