## 10. Safety

All safety analyses will be performed for the Safety population (SAF) and will be reported by treatment group as well as ZX008 combined for the 16-week treatment period unless noted otherwise.

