**Statistical Analysis Plan**

Sponsor: Zogenix International Limited; Protocol No.: ZX008 Study 2 (ZX008-1501 and ZX008-1502)

A table will be provided for TEAEs (preferred term) where the percentage of subjects in a ZX008 arm who experience the event exceeds the percentage of subjects in the Placebo group with the event and occurs with a frequency of at least 2%.

No inferential statistical methods (i.e., methods that yield p-values) will be used to compare treatment groups on the frequency or severity of AEs.

These summaries will be provided for the T+M period.

Additionally, the following listings will be produced for all enrolled subjects:

- All AEs, events considered to be TEAE will be identified in the listing
- Serious AEs
- AEs that lead to premature discontinuation from the study
- Deaths

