**Statistical Analysis Plan**

Sponsor: Zogenix International Limited; Protocol No.: ZX008 Study 2 (ZX008-1501 and ZX008-1502)

Neuropsychiatric
1. Serotonin syndrome (At least 3 of following symptoms must be present: Agitation, restlessness, confusion, both increased HR and blood pressure, dilated pupils, muscle twitching, muscle rigidity, hyperhidrosis, diarrhea, headache, shivering, tremors, both nausea and vomiting)
2. Hallucinations
3. Psychosis
4. Euphoria
5. Mood disorders: depression and anxiety if they rise to a level of a disorder
6. Suicidal thoughts, ideation or gestures
Genitourinary
1. Priapism

MedDRA SMQs will be employed as applicable to identify each AESI category or manually assigned through review. This will be completed and documented prior to study unblinding.

Adverse events of special interests will be summarized by treatment group and by system organ class and preferred term for the T+M Period.

All adverse events of special interest will listed separately.

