**Statistical Analysis Plan**

Sponsor: Zogenix International Limited; Protocol No.: ZX008 Study 2 (ZX008-1501 and ZX008-1502)

Table	14.3.1.19	Serious Treatment-Emergent Adverse Events During Double-blind Treatment Period by MedDRA System Organ Class and Preferred Term with Number of Events and Number of Resolved Events - Safety Population
Table	14.3.1.19a	Serious Treatment-Emergent Adverse Events During Double-blind Treatment Period by MedDRA System Organ Class and Preferred Term with Number of Events and Number of Resolved Events (Japan) - Safety Population
Table	14.3.1.20	Treatment-Emergent Adverse Events Occurred More Frequent in ZX008 than Placebo ( $\geq 2\%$ ) During Double-blind Treatment Period by Preferred Term - Safety Population
Table	14.3.1.20a	Treatment-Emergent Adverse Events Occurred More Frequent in ZX008 than Placebo ( $\geq 2\%$ ) During Double-blind Treatment Period by Preferred Term (Japan) - Safety Population
Table	14.3.1.20b	Treatment-Emergent Adverse Events Occurred More Frequent in ZX008 than Placebo ( $\geq 2\%$ ) During Double-blind Treatment Period by Preferred Term (Non-Japan) - Safety Population
Table	14.3.1.21	Treatment-emergent Adverse Events with Onset During the Titration Period - Safety Population
Table	14.3.1.21a	Treatment-emergent Adverse Events with Onset During the Titration Period (Japan) - Safety Population
	14.3.2	Listings of Deaths, Other Serious and Significant Adverse Events
Table	14.3.2.1	Listing of Deaths
Table	14.3.2.2	Listing of SAEs
Table	14.3.2.3	Listing of Discontinuations Due to AE
	14.3.4	Summary of Laboratory Data
Table	14.3.4.1	Laboratory Parameters – Hematology – Safety Population
Table	14.3.4.1a	Laboratory Parameters – Hematology (Japan) – Safety Population
Table	14.3.4.1b	Laboratory Parameters – Hematology (Non-Japan) – Safety Population
Table	14.3.4.2	Laboratory Parameters – Biochemistry – Safety Population
Table	14.3.4.2a	Laboratory Parameters – Biochemistry (Japan) – Safety Population
Table	14.3.4.2b	Laboratory Parameters – Biochemistry (Non-Japan) – Safety Population
Table	14.3.4.4	Laboratory Parameters – Urinalysis – Safety Population
Table	14.3.4.4a	Laboratory Parameters – Urinalysis (Japan) – Safety Population
Table	14.3.4.4b	Laboratory Parameters – Urinalysis (Non-Japan) – Safety Population
Table	14.3.4.4.1	Laboratory Parameters – Urinalysis (Quantitative Parameters) – Safety Population

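### The SAPs give two incompatible windows for adverse event tables, and the longer one counts events that begin on ZX008 during Transition as placebo events

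*SAP*

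**What the plan says.** The Study 2 SAP is cited here. The Study 1 SAP has matching text in Sections 3.3, 5.3, 6.1.6, 6.4, 6.4.1, 6.4.1.2 and 6.4.2.

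**Text pointing to Visit 13**
- Section 10.3: "Safety tables will present TEAE data by assigned treatment group through Visit 13".
- Section 10 sets the default: safety results are "reported by treatment group as well as ZX008 combined for the 16-week treatment period unless noted otherwise".
- Section 6.5 defines the 16-week double-blind period as one "which includes 2 weeks of Titration period, 12 weeks of Maintenance period and 2 weeks of Taper/Transition period", ending at Visit 13.
- Section 2.7, Transition Period: "Subjects who had been randomized to placebo increased their dose to 0.2 mg/kg/day beginning on Day 1 of the transition". The same section keeps Taper and Transition data in the safety analyses.
- Section 5.2 analyses subjects by randomised group. Section 12 records this as a change from the protocols, which presented safety by treatment actually received.

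**Text pointing to Visit 12**
- Section 10.3, Incidence of Treatment Emergent Adverse Events, closes its list of tables with "These summaries will be provided for the T+M period". The list includes the table of terms more frequent on ZX008 than on placebo.
- Section 10.3, AESI: "Adverse events of special interests will be summarized by treatment group and by system organ class and preferred term for the T+M Period".

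**The concern.** T+M stops before any placebo subject takes study ZX008. The Visit 13 window does not. If a table is run by randomised arm to Visit 13, an event that starts in a placebo subject's first two weeks on ZX008 is printed in the placebo column.

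The placebo column is the comparator for tolerability, and the first weeks on a drug are when many adverse events may be expected. A programmer has two instructions for the same tables and no rule for choosing between them. The overview could therefore show one AESI or serious-event count and the detailed tables another.

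**Working it through.** **1. The window.** 2 + 12 + 2 = 16 weeks = 112 days, which reproduces the SAP's figure. Visit 12 is Day 99 and Visit 13 is Day 113, so Taper/Transition is 113 − 99 = 14 days, and 14/112 = 12.5% of the window.

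**2. What subjects take in those 14 days (Section 2.7)**

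| Randomised arm | Entering the extension | Tapering (not entering, or early discontinuation) |
|---|---|---|
| Placebo | ZX008 0.2 mg/kg/day, Days 1–14 | Placebo |
| 0.2 mg/kg/day | Unchanged | Placebo |
| 0.8 mg/kg/day | 0.4, then 0.2 mg/kg/day | 0.4, then 0.2 mg/kg/day |

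Misattribution to placebo is confined to placebo subjects entering the extension.

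**3. Which tables are exposed**

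| Output | Text | Index title | Reading |
|---|---|---|---|
| 14.3.1.1 overview | No T+M limit | DB Treatment Period | 16 weeks |
| 14.3.1.13–14.3.1.16 (Study 2; concomitant AED, age) | Described after the T+M sentence, no limit | Double-blind Treatment Period | 16 weeks |
| 14.3.1.20, "Treatment-Emergent Adverse Events Occurred More Frequent in ZX008 than Placebo" | T+M | Double-blind Treatment Period | Conflict |
| AESI by system organ class and preferred term | T+M | No period given | T+M |

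The overview also counts AESIs, so those events would be counted over two different windows.

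**4. One subject in Table 14.3.1.20.** A term is listed when a ZX008 arm's percentage exceeds placebo's and reaches 2%. With 40 per arm, one subject is 1/40 = 2.5%. A term at 1/40 against 0/40 is listed. One Transition event in a placebo subject makes it 1/40 against 1/40, and the term drops out unless a ZX008 arm gains an event too.

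**5. Early terminators.** Section 6.5 ends their double-blind period at the early termination visit. The Taper/Transition row of the same section runs from that visit to Visit 13, and Section 10.3 counts events through Visit 13. Their taper events are in or out depending on which text is followed.

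**6. Size, on assumed rates.** The SAPs give no adverse event rates and no roll-over rate. Let H = −ln(1 − p) be an arm's 14-week cumulative hazard, s the share of it falling in the first two weeks of exposure, f the share entering the extension (0.8 to 1.0), and h = (1 − s)H/6 the hazard over a later two weeks. Through Visit 13:

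- Placebo: f[1 − exp(−(H0 + s·H2))] + (1 − f)[1 − exp(−(H0 + h0))]
- 0.2 arm: f[1 − exp(−(H2 + h2))] + (1 − f)[1 − exp(−(H2 + h0))]
- 0.8 arm: 1 − exp(−(H8 + h2)), applied to all its subjects as a simplification

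Example with p = 10%, 20%, 40%, f = 1 and s = 0.5: H0 = 0.105, H2 = 0.223, H8 = 0.511.
- Placebo: 1 − exp(−(0.105 + 0.112)) = 19.5%.
- 0.2 arm: 1 − exp(−(0.223 + 0.019)) = 21.5%.
- 0.8 arm: 1 − exp(−(0.511 + 0.019)) = 41.1%.

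The differences are 2.0 and 21.6 points, against 10 and 30 in T+M.

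| Assumed 14-week incidence (placebo/0.2/0.8) | T+M difference, 0.2; 0.8 (points) | Visit 13, constant hazard (s = 2/14) | Visit 13, front-loaded (s = 0.5) |
|---|---|---|---|
| 10/20/40% | 10; 30 | 9.7; 29.1–29.4 | 2.0–3.6; 21.6–23.3 |
| 5/20/40% | 15; 35 | 14.5–14.6; 33.9–34.4 | 6.4–8.1; 26.1–28.0 |
| 10/15/25% | 5; 15 | 4.9; 14.7–14.8 | −0.9 to 0.3; 9.0–10.2 |

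The calculation gives the active arms two further weeks of events. It does not model extra events caused by stepping down or stopping ZX008.

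**The case against.** The 16-week window is only a default that yields where the text says otherwise, and the text does say otherwise for the system organ class and preferred term tables and for AESIs. A reader might infer from the Visit 13 sentence that every TEAE table is contaminated. The documents do not support that.

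Index titles are also weak evidence. The Study 2 index uses nearly the same double-blind label for seizure-frequency tables, from which Section 2.7 excludes Taper and Transition data except where specified. Section 6.5 itself offers several end dates for the period. These points stand, which is why Table 14.3.1.20 is a conflict and not a settled error. They do not help the overview or the subgroup tables, where nothing overrides the default.

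A reader might also infer that every ZX008-minus-placebo difference is pulled toward zero. That does not follow. Tables run on T+M are unaffected. In the others the active arms also gain two weeks of events, and step-down events in the 0.8 arm could offset some of the loss.

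The stakes are limited too: efficacy is untouched apart from any stated exception, no p-values are planned for adverse events, all events are listed, and Study 2 has a separate titration-onset table (14.3.1.21).

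**Conclusion.** The SAPs contradict themselves on the window for adverse event tables, and one of the two windows misattributes events. This should be fixed.

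The documents alone establish that up to 14 of 112 days for a placebo subject entering the extension are on ZX008 and are counted as placebo under the Visit 13 window. They also establish that this reaches Table 14.3.1.1 and the Study 2 subgroup tables, and that the text and title of Table 14.3.1.20 disagree. The extra days can only raise the placebo percentages.

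The net change in the difference between arms is not established. It rests on assumed incidences, hazard shape and roll-over. Across the three sets shown, the loss is 0.1 to 1.1 points with constant hazard and 4.7 to 8.9 points if half the hazard falls in the first two weeks of exposure. For the 10/20/40% set, it is under 1 point and about 6 to 8 points.

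**What to change.** - Use T+M (first dose through Visit 12 or early termination) for every between-arm TEAE, SAE and AESI table, including 14.3.1.1 and all tables titled for the double-blind period.
- Report Taper/Transition events for all subjects, early terminators included, in a separate table by the treatment actually taken in that period.
- Reconcile Sections 6.5, 10 and 10.3 of the Study 2 SAP, Sections 6.1.6, 6.4, 6.4.1 and 6.4.1.2 of the Study 1 SAP, and the index titles, so that each table names one window.

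The cost is SAP wording, a date filter and one extra table. No new data are needed.
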